9.5 Withdrawal of study participants

In general terms, all randomised study participants should remain in follow-up for the duration of the study, regardless of whether or not they continue to take randomly assigned therapy. All study participants should continue to attend all study visits and complete all study-mandated assessments as per protocol. No participants will be replaced if there is a withdrawal.

The reasons for premature study discontinuation and withdrawal of participants from the study include the following criteria:

- Termination of the study by the Protocol Steering Committee
- Withdrawal of consent - participants may revoke consent for follow-up without jeopardising their relationship with either their doctor or the Sponsor. If a participant revokes consent then, if possible, all assessments scheduled for the final visit should be completed. The date of the withdrawal of consent must be documented in the participant’s medical notes. See MOOP for more details.

10.0 Clinical & Toxicity Management Guidelines

10.1 Clinical and Toxicity Management Guidelines

Investigators and study sites are encouraged to keep participants enrolled within the protocol regardless of whether they continue on their original randomised study treatment. For the purposes of uniform assessment of adverse events (including toxicities) this protocol employs the current DAIDS Common Toxicity Grading Scale (see Appendix 1). In this protocol bleeding events will be graded according to the Bleeding Academic Research Consortium (BARC) definitions for bleeding (see Appendix 2). Any neurological event should be investigated to rule out bleeding as an underlying cause. Any event with neurological symptoms and signs that is linked to bleeding of the central nervous system will be graded according to the BARC scale and managed as outlined in section 10.3.2. Neurological events without bleeding should be graded using the DAIDS scale and managed as clinically indicated.

This systematic approach is intended to also provide a framework for clinical management of emergent adverse events after randomisation as described in 10.2 below. These recommendations are guidelines that do not override sound and qualified clinical judgement.

10.2 Dose modifications

No vorapaxar dose modifications should be made in response to observed toxicities. If vorapaxar is suspected in the etiology of a significant adverse event then dosing should cease immediately. This could apply if an event unrelated to vorapaxar could be worsened as a consequence of continued exposure to the study drug. Rechallenge can occur if or when clinically appropriate.

10.2.1 DAIDS Grade 1 or 2 adverse events

Participants who develop a Grade 1 or 2 adverse event or toxicity may continue the study drug without modification. Participants experiencing Grade 1 or 2 adverse events who choose to discontinue the study drug should remain on study and continue to undergo protocol-mandated evaluations and assessments.

10.2.2 DAIDS Grade 3 adverse events

If the investigator has compelling evidence that the adverse event has NOT been caused by the study drug, dosing may continue. Participants who develop a Grade 3 adverse event or toxicity considered to be possibly, probably or definitely related to the study drug (including raised AST/ALT levels in the presence of clinical symptoms) should have study drug withheld, at the investigator's discretion. The participant should be re-evaluated regularly until the adverse event returns to Grade ≤ 2 , at which time the study drug may be reintroduced at the discretion of the investigator or according to standard practice.

If the same Grade 3 adverse event recurs within four weeks, study drug must be permanently discontinued if the investigator considers the adverse event related to study drug. However, if the same Grade 3 adverse event recurs after four weeks, the management scheme outlined above may be repeated.

Participants experiencing Grade 3 adverse events requiring permanent discontinuation of study drug therapy should be followed regularly (weekly is suggested) until resolution of the adverse event. Participants should remain in follow-up and continue to attend for protocol-mandated assessments and evaluations.

10.2.3 DAIDS Grade 4 adverse events

Participants who develop a Grade 4 adverse event or toxicity considered to be possibly, probably or definitely related to the study drug will have the study drug temporarily discontinued. The AE should be resolved before any decision is made to rechallenge the subject with the study drug. Participants experiencing Grade 4 AEs requiring permanent discontinuation of study drug therapy should be followed regularly (weekly is suggested) until resolution of the adverse event. The patient should remain on study and continue to undergo protocol-specified evaluations and assessments.

Participants with Grade 4 asymptomatic or non-significant laboratory abnormalities may continue study drug therapy if the investigator has compelling evidence that the toxicity is NOT related to the study drug(s). However, if a participant develops a Grade 4 AST/ALT adverse event, without clinical symptoms, must have their study drug permanently discontinued. The participant should remain in follow-up and continue to attend for protocol-mandated assessments and evaluations.

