3.3 Vorapaxar

Vorapaxar sulphate (Zontivity™) is a first in class, tricyclic himbacine-derived selective inhibitor of platelet aggregation mediated by PAR-1.

Vorapaxar has been developed in a number of primary and secondary care settings for cardiovascular diseases. In the setting of acute coronary syndromes vorapaxar did not affect a composite primary endpoint that included death, MI, stroke, recurrent ischemia or coronary revascularisation but did significantly

increase the risk of major bleeding including intracranial haemorrhage¹¹. In a further study that followed 26,449 patients with a history of MI, cerebral stroke or peripheral arterial disease, vorapaxar significantly reduced the risk of cardiovascular disease mortality and ischemic events among patients with stable atherosclerosis while also increasing the risk of moderate to severe bleeding including intracranial haemorrhage¹². This study identified the risk of severe bleeding among patients with a history of stroke – which would now be regarded as contraindicated for treatment with vorapaxar and therefore participation in this study. Importantly, the findings arose among a patient group who were also receiving standard secondary prophylaxis for CVD (88% receiving aspirin and 78% receiving thienopyridine) and so the effects reflect adjunctive use to already potent anti-thrombotic therapy. The hazard ratio (95% CI) for vorapaxar recipients relative to placebo recipients for the primary endpoint (fatal CV event, MI or stroke) was 0.87 (0.80-0.94; $p < 0.001$). A total of 2204 patients experienced a primary event over three years, 1028 (9.3%) vorapaxar recipients and 1176 (10.5%) of placebo recipients. Moderate or severe bleeding occurred in 4.2% of patients who received vorapaxar and 2.5% of patients who received placebo (HR, 1.66; 95% CI 1.43–1.93; $p < 0.001$).

Vorapaxar has now been licensed in the USA as secondary prophylaxis for patients with a history of MI or peripheral arterial disease except ischemic stroke.

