7.1 Eligibility criteria

Inclusion criteria

1. HIV-1 positive by licensed diagnostic test
2. aged ≥ 40 years
3. plasma HIV RNA < 50 copies/mL for at least 24 weeks
4. screening CD4+ cell count > 50 cells/mm³
5. treated for at least 12 weeks with a suppressive regimen of combination antiretroviral therapy that does not include HIV protease inhibitors and/or NNRTIs (except rilpivirine)
6. plasma d-dimer > 200 ng/mL mL (> 0.2 µg/mL or > 0.2 mg/L) fibrinogen equivalent units or > 100 ng/mL (> 0.1 µg/mL or > 0.1 mg/L) d-dimer units in the absence of established cause (deep vein thrombosis/embolism)
7. provision of written informed consent

Exclusion criteria

1. Absolute neutrophil count (ANC) < 1000 cells/µL
2. haemoglobin < 10.0 g/dL
3. platelet count $< 75,000$ cells/µL
4. AST and/or ALT > 2.5 x ULN
5. estimated glomerular filtration rate < 30 mL/min/1.73m²) using CKD-EPI (Chronic Kidney Disease Epidemiology Collaboration) equation
6. history of myocardial infarction or unstable atherosclerotic disease
7. history of ischemic stroke or transient ischaemic attack (TIA)
8. active peptic/duodenal ulcer or other bleeding disorder within the previous 12 months

9. intent to have surgery within the 6 month period after randomisation
10. current use of aspirin or P2Y12 antiplatelet therapy
11. current use of anticoagulants, (e.g. heparin or warfarin), fibrinolytic therapy, chronic (more than 5 consecutive days) nonsteroidal anti-inflammatory drugs (NSAIDs), strong CYP3A4 inhibitors or inducers. See Manual of Operations for full list of medications to avoid.
12. participants unlikely to be able to remain in follow-up
13. pregnant or nursing mothers
14. in the clinical judgement of the investigator, participation in this trial is deemed inappropriate as this may conflict with the well-being of the participant

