Myalgia (generalized)	Muscle pain causing no or minimal interference with usual social & functional activities	Muscle pain causing greater than minimal interference with usual social & functional activities	Muscle pain causing inability to perform usual social & functional activities	Disabling muscle pain causing inability to perform basic self-care functions
Osteonecrosis	NA	No symptoms but with radiographic findings AND No operative intervention indicated	Bone pain with radiographic findings OR Operative intervention indicated	Disabling bone pain with radiographic findings causing inability to perform basic self-care functions
Osteopenia⁶ ≥ 30 years of age	BMD t-score -2.5 to -1	NA	NA	NA
< 30 years of age	BMD z-score -2 to -1	NA	NA	NA
Osteoporosis⁶ ≥ 30 years of age	NA	BMD t-score < -2.5	Pathologic fracture (e.g., compression fracture causing loss of vertebral height)	Pathologic fracture causing life-threatening consequences
< 30 years of age	NA	BMD z-score < -2	Pathologic fracture (e.g., compression fracture causing loss of vertebral height)	Pathologic fracture causing life-threatening consequences

⁶ BMD t and z scores can be found in: Kanis JA on behalf of the World Health Organization Scientific Group (2007). Assessment of osteoporosis at the primary health-care level. Technical Report. World Health Organization Collaborating Centre for Metabolic Bone Diseases, University of Sheffield, UK. 2007: Printed by the University of Sheffield.

Neurologic

PARAMETER	GRADE 1 MILD	GRADE 2 MODERATE	GRADE 3 SEVERE	GRADE 4 POTENTIALLY LIFE-THREATENING
Acute CNS Ischemia	NA	NA	Transient ischemic attack	Cerebral vascular accident (e.g., stroke with neurological deficit)
Altered Mental Status (for Dementia, see Cognitive, Behavioral, or Attentional Disturbance below)	Changes causing no or minimal interference with usual social & functional activities	Mild lethargy or somnolence causing greater than minimal interference with usual social & functional activities	Confusion, memory impairment, lethargy, or somnolence causing inability to perform usual social & functional activities	Delirium OR Obtundation OR Coma

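### After an on-study ischaemic stroke judged related, section 10.2.3 requires only a temporary stop of study drug, although section 3.3 calls a history of stroke contraindicated for vorapaxar

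*Protocol*

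**What the plan says.** Section 3.3 of the protocol reports that the large secondary-prevention trial found a risk of severe bleeding in patients with prior stroke, "which would now be regarded as contraindicated for treatment with vorapaxar and therefore participation in this study". Exclusion 7 in section 7.1 bars anyone with a past ischaemic stroke or TIA.

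For events during the study, section 10.1 sends neurological events without bleeding to the DAIDS scale and to clinical management. The neurologic table of Appendix 1 places stroke with deficit at Grade 4 and TIA at Grade 3. Section 10.2.3 then says that participants with a Grade 4 event "considered to be possibly, probably or definitely related to the study drug will have the study drug temporarily discontinued". On restarting it says: "The AE should be resolved before any decision is made to rechallenge the subject with the study drug".

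Elsewhere the protocol does write permanent stops: for any BARC type 3 bleed (10.3.2.3), for emergency surgery on study (10.3.2.4), and for a Grade 4 AST/ALT rise without symptoms (10.2.3).

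**The concern.** The entry rule and the on-study rule pull in different directions. The protocol regards prior stroke as a reason not to give the drug at all. A participant who has an ischaemic stroke at week 3, say, would be ineligible if screened the next day, yet the written rule for a related event is a temporary stop followed by a possible restart.

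What is at stake is the safety of a participant on vorapaxar, in a trial whose primary endpoint is a biomarker. A restart is hard to undo: section 8.1 gives a terminal half-life of about 8 days, and section 8.2 states that there is no known antidote and that an effect on platelets persists 4 weeks after stopping. The primary analysis is not at stake.

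**Working it through.** The point itself involves no calculation. It is settled by setting the provisions side by side.

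**Step 1: which rule governs.** An ischaemic stroke without bleeding goes to DAIDS grading under 10.1, is Grade 4 under Appendix 1, and so falls under 10.2.3. A haemorrhagic stroke is different: it is a BARC type 3c bleed and carries a permanent stop. Appendix 2 leaves haemorrhagic transformation outside type 3c, so that rule would not catch this complication of an ischaemic stroke.

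**Step 2: whether any provision requires a permanent stop after a first ischaemic stroke.**

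| Provision | What it does | Permanent stop required? |
|---|---|---|
| 10.2.3, event judged related | Temporary stop; rechallenge may be decided after resolution | No |
| 10.2.3, clinical event judged unrelated | No instruction either way | No |
| 10.2 | Immediate stop if the drug is suspected; can also apply to an unrelated event that exposure could worsen; rechallenge allowed when clinically appropriate | No |
| 10.4 | Mandatory stop, whatever the cause, if the investigator thinks continuing is not in the participant's interest; the section covers temporary and permanent stops | Not required |
| 8.2 | Immediate stop if anticoagulants, fibrinolytics or other listed drugs are needed; restart as soon as clinically possible, with safety paramount | No |
| 11.2.1, 11.4 | Stroke reported in the same way as a serious adverse event; project team and Medical Officer review | No |
| 18.0 | Scheduled DSMB safety reviews; ad hoc triggers are BARC type 2 and 3 bleeds | No |

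**Step 3: comparison with the protocol's own practice.** Several entry exclusions have an on-study counterpart: surgery (exclusion 9 and 10.3.2.4), listed medications (exclusion 11 and 8.2) and pregnancy (exclusion 13 and 11.5). The laboratory exclusions do not. Stroke, the history that section 3.3 names as contraindicated, has none.

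**Step 4: exposure.** With 30 participants per arm and 12 weeks of dosing, vorapaxar exposure is 30 × 12/52 = 6.9 person-years. The documents give no stroke rate to multiply this by.

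**Step 5: cost of a permanent-stop rule to power.** Inputs from section 6.1: SD of change 0.4, correlation 0.5 between weeks 8 and 12, difference 0.26 log₁₀.

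- SE = 0.4 × √((1 + 0.5)/2) × √(2/n per arm); power = Φ(difference/SE − 1.96).
- The plan's own figure, n = 28: SE = 0.0926. For 0.26, Φ(2.808 − 1.96) = 80.2%. For 0.30, Φ(3.240 − 1.96) = 90.0%. Both match the stated 80% and 90%.
- n = 30: SE = 0.0894; Φ(2.907 − 1.96) = 82.8%.
- One of 30 vorapaxar participants stops and loses all effect: 0.26 × 29/30 = 0.2513; Φ(2.810 − 1.96) = 80.2%.

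**The case against.** The best reply is that the protocol already leads a sensible investigator to stop. Section 10.2 reaches even a stroke judged unrelated if exposure could worsen it. Section 10.4 is mandatory and does not depend on causality. A participant put on continuing anticoagulation could not restart under 8.2. Section 10.2.3 recognises that some Grade 4 events need permanent discontinuation, and a stroke with deficit must resolve before rechallenge is considered, inside a 12-week period that section 8.0 does not extend. An investigator who has read section 3.3 would hardly find rechallenge appropriate. Serious adverse event review and scheduled DSMB reviews sit on top. All of this stands, and it makes the restart path narrow. It does not close the path, because in each case permanence rests on judgement.

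Three stronger readings are tempting, and the documents do not support them.

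- *That dosing is expressly permitted to continue after an unrelated stroke.* The only such permission in 10.2.3 is narrower: "Participants with Grade 4 asymptomatic or non-significant laboratory abnormalities may continue study drug therapy". A clinical stroke is outside it.
- *That TIA is the same contradiction.* Section 10.2.2 does say: "If the investigator has compelling evidence that the adverse event has NOT been caused by the study drug, dosing may continue", and it allows reintroduction. But section 3.3 does not name TIA, exclusions are not always mirrored by stop rules, and 10.2.2 requires a permanent stop if a related event recurs within four weeks. For a first TIA only exclusion 7 remains.
- *That the bleeding increases quoted in the protocol measure the hazard.* The 55% in section 10.3.2 comes from patients without prior stroke or TIA. Of its trial findings, section 3.3 says that "the effects reflect adjunctive use to already potent anti-thrombotic therapy", with 88% of patients on aspirin, which exclusion 10 bars here.

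**Conclusion.** The point holds for ischaemic stroke, as a minor safety inconsistency. The rule stated for a related Grade 4 event does not fit the protocol's own contraindication, and no other provision requires the stop to be permanent. The chance that it would matter is low: exposure is about 6.9 person-years, and most investigators would probably stop the drug for good. The documents do not let one put a figure on that chance or on the bleeding risk that would follow a restart. The conclusion rests on the protocol and SAP alone. The Manual of Operations and the Investigator Brochure are not among the documents and could contain such a rule. No efficacy result turns on this.

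**What to change.** Add to section 10.4, cross-referenced from 10.2.3 and 8.2:

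> Any on-study ischaemic stroke requires immediate and permanent discontinuation of study drug regardless of judged causality, with no rechallenge; the participant remains in follow-up and in the mITT analysis.

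The cross-reference in 8.2 should say that its direction to restart does not apply after such an event. Adding a first TIA is optional.

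The cost is a sentence or two in an amendment and, at most, a rare early stop. Section 9.5 already keeps such a participant in follow-up, and SAP section 1.3 already keeps the data in the mITT analysis. The loss of about 2.6 percentage points of power shown above is the worst case for one vorapaxar participant, and power would still be about the planned 80%.

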10.4 Discontinuation of study treatment

In general terms, all randomised study participants should aim to take the study treatment as per protocol. However, reasons for either temporarily or permanently ceasing study treatment include:

- Disease progression requiring medical intervention
- Surgical intervention
- Administration of prohibited therapy
- Investigator or participant wish to stop therapy
- Occurrence of unacceptable adverse drug reactions

Participants MUST be discontinued from study treatment if there is any clinical adverse event, laboratory abnormality or intercurrent illness that in the opinion of the investigator indicates that continued treatment with study therapy is not in the best interest of the participant.

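### Protocol 10.2.3 words the permanent stop for Grade 4 AST/ALT so that it covers only participants without symptoms: a probable drafting slip with very small practical effect

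*Protocol*

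**What the plan says.** Protocol 10.2.3 contains three rules that bear on a Grade 4 AST/ALT event.

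- The general rule: a Grade 4 event judged "possibly, probably or definitely related to the study drug will have the study drug temporarily discontinued". On restarting: "The AE should be resolved before any decision is made to rechallenge the subject with the study drug".
- A permission: "Participants with Grade 4 asymptomatic or non-significant laboratory abnormalities may continue study drug therapy if the investigator has compelling evidence" that the study drug is not the cause.
- An exception to that permission, placed directly after it: "However, if a participant develops a Grade 4 AST/ALT adverse event, without clinical symptoms, must have their study drug permanently discontinued". It sets no condition on relatedness.

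The Grade 3 rule in 10.2.2 brings in symptoms from the other side. Related Grade 3 events, "including raised AST/ALT levels in the presence of clinical symptoms) should have study drug withheld", at the investigator's discretion.

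Sections 10.1, 10.2 and 10.4 add general provisions that apply at any grade. The SAP does not deal with stopping rules.

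**The concern.** Among Grade 4 transaminase rises, one with symptoms is the more worrying presentation. As worded, the only compulsory permanent stop attaches to the presentation without symptoms. An investigator who follows the text to the letter must bar the well participant from further drug, yet may consider rechallenge in the symptomatic one.

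What is at stake is participant safety within a 12-week dosing period. The protocol lacks a firm bar on rechallenge after a related symptomatic Grade 4 event, and a specific instruction for a symptomatic event put down to another cause. With about 7 centres in two countries, sites should not have to infer the intended rule.

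**Working it through.** The plan states no figure to reproduce. The check crosses symptoms with relatedness and reads off what 10.2.3 requires in each of the 2 x 2 = 4 cases.

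| Grade 4 AST/ALT event | Literal rule in 10.2.3 | General provisions elsewhere |
|---|---|---|
| No symptoms, related | Permanent stop | Not needed |
| No symptoms, unrelated | Permanent stop (the exception overrides the permission to continue) | Not needed |
| Symptoms, related | Temporary stop; rechallenge may be decided after resolution | 10.2 requires immediate cessation but also allows rechallenge |
| Symptoms, unrelated | No specific rule | 10.2 and 10.4, by judgement |

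So 2 of the 4 cases carry the compulsory permanent stop, and both are the asymptomatic ones.

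**Do other sections close the two symptomatic cases?** Section 10.2 stops dosing when vorapaxar is suspected. For events with another cause it adds: "This could apply if an event unrelated to vorapaxar could be worsened as a consequence of continued exposure to the study drug". It then says: "Rechallenge can occur if or when clinically appropriate". Section 10.4 is firmer: "Participants MUST be discontinued from study treatment if there is any clinical adverse event, laboratory abnormality or intercurrent illness". That duty depends, however, on the investigator's opinion that continuing is not in the participant's interest. Section 10.1 makes all of these guidelines subject to clinical judgement. Together they permit a permanent stop in the symptomatic cases, but none requires one.

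**What was probably meant?** The exception opens with a contrast word and follows a permission that concerns asymptomatic or non-significant laboratory abnormalities. Section 11.1 says that isolated laboratory abnormalities without symptoms are generally not recorded as adverse events, so the asymptomatic case needed explicit mention. The sentence is also grammatically incomplete. All this points to an intended sense of *even without clinical symptoms*.

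**When could the wording change what happens to a participant?**

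- Scheduled AST/ALT tests fall at screening and weeks 0, 12 and 18 (section 2.0; sections 9.1.2, 9.2.2 and 9.3.2). Of the visits at weeks 1, 4 and 8, 0 of 3 include them.
- Dosing ends at the week 12 visit and is not extended for missed days (section 8.0). For a rise found at that visit, a temporary and a permanent stop come to the same thing. The 2-week visit window does not alter this, because dosing stops at the visit itself.
- During dosing, the rule can therefore act only on an unscheduled test, or on a week 0 result that becomes available around the first doses.
- Entry excludes AST or ALT above 2.5 x ULN (section 7.1), and Grade 4 starts at 10 x ULN (Appendix 1). A participant at the entry limit would need a 10 / 2.5 = 4-fold rise, and others more.
- Sections 10.3.1 and 10.3.3 list no hepatic reaction to vorapaxar.

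**Does it reach the analysis?** Participants who stop drug stay in follow-up (section 10.2.3), and SAP 1.3 uses all available follow-up whether or not drug was continued. Neither the sample size nor the primary comparison depends on this rule.

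**The case against.** The best defence is that, in context, the sentence is a plain exception. It removes AST/ALT from a permission that concerns asymptomatic abnormalities, so it names asymptomatic cases. No sensible investigator would take an instruction to stop even when the participant is well as licence to be lenient when the participant is ill. This stands as an account of intent, and it is why the point is a wording correction and not a charge of unsafe design.

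It also disposes of two stronger readings that a reader might infer. One is that the protocol reverses its own Grade 3 logic. That holds only on the literal reading. On the likely intended one, the rules escalate with grade: at Grade 3 symptoms support a discretionary withhold, and at Grade 4 no symptoms are needed for a permanent stop. The other is that participants with symptomatic liver injury would be kept on drug. The documents do not support this. Drug is stopped in every related case. In unrelated cases, the permission to continue in 10.2.3 does not extend to a significant symptomatic event, and 10.2 and 10.4 give grounds to stop.

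A second objection is that correcting the sentence goes too far, because it would force a permanent stop on a symptomatic case clearly due to something else. The loss of discretion is real. But the sentence already forces a permanent stop on asymptomatic cases whatever their cause, so the correction only treats symptomatic cases the same way.

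The defence does not remove the gap itself. Nothing in section 10 requires a permanent stop in a symptomatic Grade 4 AST/ALT case, and the sponsor evidently chose compulsory wording here to limit discretion.

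**Conclusion.** The point holds as a minor wording fault in an operative safety rule. Literally read, 10.2.3 leaves rechallenge open in the related symptomatic case and gives no specific instruction in the unrelated symptomatic case.

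The size is very small. For the related case to matter, an unscheduled test during dosing must show at least 10 x ULN with symptoms, the event must resolve before the week 12 visit, and the investigator must then choose to rechallenge. The documents give no rate for such events, so no expected number is offered.

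That the wording is a slip is an inference from the structure of the section; the protocol does not state the intent. If the literal text was intended, no reason is given for the stricter handling of the well participant, so the sentence needs attention on either reading.

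**What to change.** In section 10.2.3, change the opening of the sentence to *However, any participant who develops*, and change *without clinical symptoms* to *with or without clinical symptoms*. Leave the rest of the sentence as it is. In particular keep the term *adverse event*, because section 11.1 distinguishes adverse events from isolated laboratory abnormalities.

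Send sites a short memo if any participant is still dosing. The SAP, dated 13 November 2017, describes trial follow-up as already known to be excellent (SAP 1.3), so dosing may well have ended. In that case only the text correction remains useful.

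The cost is a few words and possibly one memo, with no new visit, test or data item. The one downside is that investigators lose discretion to continue or rechallenge in symptomatic cases due to another cause.
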